#### **9.3.4. Missing and Partial AE Onset Dates**

See Section [6.8.3](#).

#### **9.3.5. Summaries of Adverse Incidence Rates per 100 Person-Years of Exposure to Study Treatment**

For this study, the duration of exposure to study treatment may vary due to differential follow-up. Because of this, certain AE tables will be repeated using the number of AEs per 100 person-years of exposure instead of as a count, where 1 year = 365.25 days.

To determine 100 person-years of exposure, the duration of treatment exposure will be computed for each subject and then summed across subjects to obtain the 100 person-years exposure per treatment group. The table will then display the rate per 100 person-years of exposure (count of AEs reported/total exposure for the treatment group in 100 person-years) values for each treatment group and for each AE.

The following summary tables of rate of TEAEs per 100 person-years of exposure will be provided by treatment group (by SOC and PT):

- Summary of TEAE rate per 100 person-years of exposure
- Summary of drug-related, TEAE rate per 100 person-years exposure
- Summary of TESAEs

A listing of 100 person-years of exposure to study treatment will be provided.

#### 9.4. Total Duration of Therapy, Average Daily Dose, Maximum Daily Dose, Final Daily Dose of Study Medication, and Compliance

The number of subjects exposed to study drug will be presented on the disposition table, and the duration of exposure will be presented on the exposure table. Treatment adherence, dose interruptions, and reasons for dose interruptions will be provided as summaries and listed.

A summary and listing of dose reductions will be produced. The listing will include information of study day of dose reduction.

The number of subjects exposed to study treatment and number of subjects who discontinue treatment early will be presented on the disposition table. A summary of exposure to study treatment will be also be presented and will include a summary of 100 person-years of exposure to study treatment as described in Section 9.3.5. Listings of exposure to study treatment and of drug accountability will be provided by subject and treatment. Kaplan-Meier plots of duration of study treatment will be provided.

Treatment compliance, based on drug accountability information as collected in the eCRF, will be calculated for each study treatment that the subject received as follows:

$$\text{Treatment compliance (dispensing)} = \frac{\text{Number of capsules taken}}{\text{Expected number of capsules taken}} * 100$$

The number of capsules taken is derived from the number of capsules dispensed (30 per bottle dispensed) – the number of capsules returned as reported in the eCRF. For those on the 150 mg dose level, the expected number of capsules taken is defined relative to the lot of drug received as the number of pills taken × the duration of study treatment (eg, date of the last dose – date of the first dose + 1). The number of pills taken is either 3 or 1 depending on lot number. If a subject receives drug from different lots, the expected number of capsules taken is calculated relative to the dispense and return dates for a given lot and then summed across lots. On a date of return, the dose is assumed to be taken from the newly dispensed bottle. For subjects on the 110-mg dose level, the expected number is defined as 1 × the duration of study treatment.

A categorical summary of treatment compliance will be produced with the following categories shown in Table 9.

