9.2. Description of Study Drug Packaging, Labeling, and Storage

The study drug will be packaged in bottles. As the pharmaceutical development program for BCX7353 progresses, alternate packaging configurations may be introduced. Subjects will be dispensed a sufficient number of capsules to cover at least a 1-month dosing period. Additional visits for dispensing of study drug supply may occur after Week 24 as needed.

Each container of study drug will be labeled with the information required per local law and may include: Sponsor name, study protocol number, description of the contents including mg strength, a statement regarding the investigational (clinical trial) use of the study drug, expiry date, and kit treatment number.

Study drug must be stored between 15°C and 25°C (room temperature).

Details on the study drug packaging, labeling, shipment, storage and dispensing will be provided in the Investigational Medicinal Product (IMP) manual.

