9.3. Treatment Allocation and Study Drug Blinding

This is an open-label study. Subjects will receive BCX7353 150 mg administered orally QD.

Sites will request a kit allocation for eligible subjects in the interactive (web) response system (IXRS), preferably after all baseline assessments to confirm eligibility have been completed. If required by site procedures (i.e., dispensing of allocated study drug must occur through a pharmacy), the request may be made on the business day prior to the planned baseline visit.

During the conduct of the study, responsibility for kit supply and resupply may be transferred to a specialty pharmacy selected by the Sponsor and subjects may receive study drug directly from the specialty pharmacy. Detailed instructions will be provided at the time of implementation.

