10.3.5. End of Study Visit

Subjects who discontinue study drug will return to the clinic 3 weeks (21 ± 3 days) after the date of their last dose for their end of study or withdrawal assessment. Subjects who discontinue study drug must undergo all study-related procedures outlined in [Table 3](#). Subjects who discontinue the study but will continue to receive BCX7353 via another mechanism will have end-of-study assessments performed at their last regularly scheduled visit.

If an AE is ongoing at the end of study visit, additional clinic visit(s) or telephone contact(s) may be warranted (see Section [12.1.2](#)).

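### For 150 mg subjects with more than one lot, SAP 9.4 counts expected capsules by dispense and return dates, which can include off-drug days and count shared days twice

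*SAP*

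**What the plan says.** SAP section 9.4 divides capsules taken by capsules expected and sorts the result into the Table 9 categories: under-dosing below 80%, acceptable from 80% to below 90%, good from 90% to 110%, over-dosing above 110%. Capsules taken are those dispensed minus those returned.

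The denominator has three forms.

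- **110 mg:** one capsule for each day of study treatment.
- **150 mg, one lot:** the daily count times "the duration of study treatment (eg, date of the last dose – date of the first dose + 1". On the daily count the SAP says "The number of pills taken is either 3 or 1 depending on lot number".
- **150 mg, different lots:** "the expected number of capsules taken is calculated relative to the dispense and return dates for a given lot", summed across lots.

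A further sentence assigns the dose on a return date to the newly dispensed bottle. Nothing says that the last lot stops at the last dose, or how to count days on which two lots are held.

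In the protocol, section 10.3.5 brings subjects who stop study drug back 21 ± 3 days "after the date of their last dose for their end of study or withdrawal assessment". Section 9.4 asks subjects to bring all used and unused kits to each visit. Section 9.2 allows extra dispensing visits after Week 24. Section 9.3 foresees that "subjects may receive study drug directly from the specialty pharmacy".

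**The concern.** A return date is not a last-dose date. If a subject stops drug and hands in the final bottles at the end-of-study visit, the dispense-to-return interval of the last lot contains about three weeks in which no capsule was due. If a new lot arrives while an older one is still out, the two intervals overlap and the shared days enter the expected count twice. Either way the denominator grows while the numerator does not, so a subject who took every dose scores below 100%.

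The off-drug effect is largest in relative terms for subjects who stop early, a group of interest for tolerability. The lot rule also exists only at 150 mg, so in a display by dose group it could create a small apparent difference in compliance between doses. Two subjects with the same dosing history could receive different percentages only because one of them changed lots.

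**Working it through.** The plan gives no compliance figure to reproduce. The check applies the SAP 9.4 formula to a subject who takes every dose.

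**Inputs**

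- Category limits: SAP Table 9.
- Daily count at 150 mg, 1 or 3 by lot: SAP 9.4.
- Gap from last dose to the end-of-study visit, 18 to 24 days with target 21: Protocol 10.3.5 and SAP Table 3. That the last lot comes back only at this visit is an assumption.
- 12, 48 and 96 weeks = 84, 336 and 672 days.
- An 84-day overlap of lots is an assumption: one 12-week interval, or half of a 24-week interval between visits in the current protocol.

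**1. No gap and no overlap**

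- One lot, one capsule per day, 672 days: 672/672 = 100%.
- Consecutive lots, 336 days at 3 and then 336 at 1, exchange day counted once: 1,344/1,344 = 100%.

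**2. Last lot counted to a return 21 days after the last dose, one capsule per day**

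Compliance = D/(D + 21), where D is days of dosing. It is below 0.80 when D < 4 × 21 = 84.

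| D (days) | Taken/expected | Compliance | Category |
|---|---|---|---|
| 56 | 56/77 | 72.7% | Under-dosing |
| 83 | 83/104 | 79.8% | Under-dosing |
| 84 | 84/105 | 80.0% | Acceptable |
| 168 | 168/189 | 88.9% | Acceptable |
| 336 | 336/357 | 94.1% | Good |
| 672 | 672/693 | 97.0% | Good |

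If the return day is not counted, the excess is 20 days and the cut-off is D < 80. Gaps of 18 and 24 days give cut-offs of 72 and 96 days.

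**3. Same gap, last lot at three capsules per day**

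The excess is 3 × 21 = 63 capsules, so the score is below 80% when fewer than 4 × 63 = 252 capsules were taken in total.

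- 28 days at 1, then 28 at 3: taken 28 + 84 = 112; 112/175 = 64.0%, Under-dosing.
- 84 days at 1, then 84 at 3: taken 84 + 252 = 336; 336/399 = 84.2%, Acceptable.

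**4. Two lots held over the same 84 days, one capsule per day**

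Compliance = D/(D + 84k) for k overlaps.

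- k = 1, D = 336: 336/420 = 80.0%, Acceptable.
- k = 1, D = 672: 672/756 = 88.9%, Acceptable.
- k = 2, D = 672: 672/840 = 80.0%, Acceptable.
- k = 3, D = 672: 672/924 = 72.7%, Under-dosing.

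One overlap alone gives under-dosing only when D < 4 × 84 = 336 days.

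**5. After the correction**

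With the last lot ended at the last dose and each day counted once, the excess is zero and every case above returns to 100%.

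**The case against.** The strongest reply is that the lot clause only apportions days. It follows directly on the first-to-last-dose definition and the statement that lots differ in capsules per day, and it says the count is relative to the dispense and return dates. Its purpose is plausibly to decide how many days run at 3 capsules and how many at 1. The sentence on the return date fits this reading and removes double counting on the exchange day. Had all 7 exchange days among 8 lots been counted twice, the result would still be 672/679 = 99.0%.

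This probably describes the intent, but the text does not secure it. At the final return there is no newly dispensed bottle, so the exchange-day sentence does not apply, and it settles one day, not weeks in which two lots are held.

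The overlap case also depends on supply. Under the SAP's 12-weekly visits, with kits brought back each time, consecutive lots need not overlap. The scenario needs two lots dispensed together, an old lot kept past a visit, or the current protocol's longer visit gaps with between-visit supply, which is only a possibility. The SAP's protocol chronology ends at Version 5.0. This limits how often overlap is likely, but it does not supply a rule for when it occurs.

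The reply on consequence stands in full. Effectiveness and safety are analysed in the safety population, person-year rates use exposure duration, and dose interruptions and discontinuations have their own displays. None of these uses the compliance percentage.

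**Conclusion.** The denominator for multi-lot 150 mg subjects needs a correction, and it is a minor one. As written, it can score a fully adherent subject too low. At one capsule per day with a 21-day gap, under-dosing results only for stops before about Day 84 (about Day 80 if the return day is excluded). About three 84-day overlaps are needed to reach it at Week 96. These sizes assume that the last lot is returned at the end-of-study visit, or that lots are held together; the documents confirm neither and do not say how many subjects had more than one lot.

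A reader might infer more than the documents support:

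- **That the compliance formula as a whole is faulty.** Single-lot 150 mg subjects and all 110 mg subjects are unaffected, and under-dosing is not the usual result for the rest.
- **That the 20 of 28 lack-of-efficacy stops before Week 12 in the interim summary (Protocol 5.2.2) are misclassified.** Of those 28, 17 were on 110 mg and 11 on 150 mg. So at most 11 of the 20 could be affected, and only if they had also changed lots and returned the last one late.
- **That one overlap between Weeks 24 and 48 means under-dosing.** That interval alone gives 168/252 = 66.7%, but the sum across lots includes the first 168 days and gives 336/420 = 80.0%.
- **That the numerator shares the defect.** It is "derived from the number of capsules dispensed (30 per bottle dispensed") less returns, so unreturned capsules count as taken, and Protocol 9.2 says "alternate packaging configurations may be introduced". That is a general limit of pill counts, it pushes the score upward, and it is separate from the lot rule.

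**What to change.** In SAP 9.4, for 150 mg subjects with more than one lot, replace the dispense-to-return count with three statements. Count each calendar day from first to last dose once. Use lot dispensing dates only to decide whether that day's expected count is 1 or 3 capsules. End the last lot at the last-dose date. All dose groups then share one definition of treatment duration.

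The cost is a few lines of SAP text and minor programming with dates already collected. No visit, data item or other analysis changes. One approximation remains: a subject who finishes an older lot after a newer one has arrived may have some days given the wrong daily count. This matters only when the two lots differ in capsules per day.

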**Table 9: Definition of Compliance Categories**

Compliance	Range of Compliance (%)
Under-dosing	< 80%
Acceptable compliance	80 to < 90%
Good compliance	90% to 110%
Over-dosing	> 110%

#### 9.5. Concomitant and Other Medications

Medications received and discontinued prior to the date of first dose are considered as prior medications. Medications will be considered as concomitant if the start date of the medication is

on or after the date of first intake of study drug for the treatment period of interest or if the start date is prior to the first date of study drug but the medication is ongoing during the treatment period in the study.

Medication verbatim text will be coded using the WHODD, DDE B2 March 2017 version. Concomitant medications will be summarized by treatment and WHO preferred name. Multiple medication use (by preferred name) will be counted once only per subject. Concomitant medications started more than 30 days post last dose will not be included in summary displays but will be listed.

Concomitant medications that were used for HAE-related indications will also be summarized separately.

### **9.5.1. Missing and Partial Concomitant and Other Medication Start and Stop Dates**

See Section [6.8.2](#).

## **9.6. Laboratory Data**

The following is a safety endpoint:

- Number and proportion of subjects who experience a treatment-emergent Grade 3 or 4 laboratory abnormality

A listing of clinical laboratory evaluations is provided in protocol Section 11.1.6.

Clinical laboratory assessments and corresponding changes from baseline will be summarized for each laboratory panel by treatment group and visit. Laboratory abnormalities will be graded according to the DMID Adult Toxicity Table (publish date: November 2007; see Protocol Appendix 16.1). Any graded abnormality that occurs following the initiation of study drug and represents at least one-grade increase from the baseline assessment is defined as treatment emergent.

Urinalysis results will be summarized by treatment and visit and listed by subject and treatment.

The number and percentage of subjects experiencing treatment-emergent graded toxicities will be summarized. Treatment-emergent Grade 3 or 4 laboratory abnormalities will be summarized separately. Laboratory toxicity shifts from baseline to worst post-baseline assessments will be summarized.

The number and percentage of subjects having elevations in liver enzyme abnormalities (alanine aminotransferase [ALT], aspartate aminotransferase [AST], or bilirubin) in relation to fold above the upper limit of normal (ULN) will be summarized by treatment group.

The following categories of abnormal hepatic laboratory values will be evaluated for any occurrence among all post baseline assessments (where “and” indicates elevations occurring at the same visit). Within each treatment group and laboratory parameter grouping, a subject may be counted once per elevation criteria using the worst-case result. That is, a subject with a worst-case ALT elevation  $>3 \times$  the ULN for a given treatment group would be counted once in the ALT  $> 1.5 \times$  ULN category and once in the ALT  $> 3 \times$  ULN category, regardless of how many ALT elevations the subject had that met the  $> 3 \times$  ULN and  $> 1.5 \times$  ULN elevation criteria.

- ALT and/or AST > 3 × ULN and total bilirubin > 1.5 or 2 × ULN
- AST > 1.5, 3, 5, 10, and 20 × ULN
- ALT > 1.5, 3, 5, 10, and 20 × ULN
- Total bilirubin > 1, 1.5, or 2 × ULN
- Alkaline phosphatase (ALP) > 1.5 × ULN

The summary display of abnormal hepatic laboratory values will be repeated for prior androgen use subgroups as defined in Section 9.2. Detailed listings of prior androgen use will be provided for subjects with any elevation in the indicated categories.

Profiles of liver enzymes and bilirubin over time will be graphically displayed for subjects with any Grade 3 or 4 abnormality in these analytes. In addition, a listing of all liver function test (ALT, AST, bilirubin, ALP, gamma-glutamyl transferase) results for subjects experiencing a treatment-emergent Grade 3 or 4 liver function test will be provided.

In addition, a Hy's law plot, a shift plot showing liver safety panel tests over time (baseline vs. on-study), and distribution plots of ALT, AST, ALP, bilirubin, cholesterol, and triglycerides over time will be produced using the format recommended by the FDA/Industry/Academia Safety Graphics working group (<https://www.ctsmedia.org/do/view/CTSpedia/StatGraphHome>). The plots to be included are the scatter plot of maximum transaminase versus maximum bilirubin, the liver test safety panel over time and the distribution of ALT by time and treatment. The distribution plots for AST, ALP, bilirubin, cholesterol and triglycerides will use the same format as is used for ALT.

Separate Kaplan-Meier plots of time to event for a Grade 3 or higher ALT, AST, or total bilirubin will be produced. The results will also be displayed in a summary table. Subjects who do not experience the event of interest will be censored at the date of the last dose.

In addition, a listing of all liver function test results for subjects experiencing a treatment-emergent Grade 3 or 4 liver function test will be provided.

A listing of AEs of nausea, vomiting, anorexia, abdominal pain, or fatigue occurring within 24 hours of an elevation of > 3 × ULN for AST or ALT will be produced.

#### **9.6.1. Complement Factors and HAE Diagnosis**

Laboratory results related to HAE diagnosis, including complement factors C1-INHAg, C1-INHf, complement 3 (C3), and C4 will be included in summaries of laboratory data. Criteria used to confirm diagnosis of HAE Type I or II will be summarized and listed as described in Section 7.6.

#### **9.6.2. Laboratory Assessments for Rash**

For subjects with rash marked as possibly, probably, or definitely related to study drug, peripheral blood mononuclear cells (PBMCs) may be collected for analysis of possible drug-specific immune responses and possible drug-responsive T-cells. The data from PBMC analysis, if collected, may be listed.

Other laboratory assessments taken at the time of baseline and at onset of rash, including clinical chemistry, hematology with differential, C3 level, and urine eosinophils will be included in laboratory listings.

### **9.7. Pregnancy**

A listing of positive pregnancy test results, if applicable, will be provided.

### **9.8. Vital Signs**

Vital signs (systolic and diastolic blood pressure, pulse rate, temperature, and respiratory rate) and body weight and corresponding changes from baseline will be summarized by treatment group and visit using descriptive statistics. These data will be listed by subject, treatment, and visit.

Distribution plots of systolic and diastolic blood pressure over time will be produced using the format recommended by the FDA/Industry/Academia Safety Graphics working group (<https://www.ctspedia.org/do/view/CTSpedia/StatGraphHome>). The graph format to be used is the same as the graph provided for the distribution of ALT by time and treatment.

### **9.9. 12-lead Electrocardiograms**

Baseline (predose) ECGs will be obtained in triplicate (ie, 3 separate readings) at 1- to 5-minute intervals, with baseline values calculated from an average of the 3 readings. All other ECGs will be single assessments. For subjects who are directly rolling over from a previous study or those with a treatment interruption of < 14 days from a previous study, the pretreatment ECG values obtained in the previous study will serve as the baseline ECG values.

An ECG should be repeated for a change from baseline in corrected QT interval using Fridericia's method (QTcF) > 60 msec or a QTcF interval > 500 msec.

ECGs and corresponding changes from baseline will be summarized by treatment group and visit using descriptive statistics.

ECG findings will be summarized.

The change from baseline in QTcF will be summarized at each time point where ECGs are analyzed. An individual subject's change from baseline will be calculated as:

$$\Delta_{ik} = (\text{QTcF for subject } i \text{ at time point } k - \text{Baseline QTcF})$$

QTcF measurements will be the average of triplicate ECGs at baseline and single values at all other time points.

For routine ECGs, the number and proportion of subjects with QTcF  $\leq 450$ , > 450 to  $\leq 480$ , > 480 to  $\leq 500$ , and > 500 msec; or changes of  $\leq 30$ , > 30 to  $\leq 60$ , or > 60 msec will be summarized. Unscheduled ECG results will be included in this summary table.

All ECG values and findings will be listed by subject, dose, and visit.

Additionally, a distribution plot of QTcF over time will be produced using the format recommended by the FDA/Industry/Academia Safety Graphics working group

(<https://www.ctspedia.org/do/view/CTSpedia/StatGraphHome>). The graph format to be used is the same as the graph provided for the distribution of ALT by time and treatment.

### **9.10. Physical Examination**

A full physical examination is conducted at screening (if applicable) and baseline, with symptom-directed examinations at all post-baseline assessments. Physical examination data will be listed by subject and dose.

### **9.11. Study Termination Status**

Study termination status will be presented on the subject disposition table.

